in aggregate in comparison to enrollees, with no personal identifiable information collected. We will also measure the participant’s weight at this initial visit.

C. Treatment assignment/randomization

Regarding randomization, we will utilize treatment allocation by minimization⁵⁵ under the direction of biostatistician [name] to reduce accidental bias/chance imbalance of key participant variables between the two groups. Minimization is a dynamic randomization technique for achieving a balance of prognostic factors across treatment groups that allows balancing over a larger number of covariates than in stratification.^{56,57} Initially, slips of paper detailing study condition (with assignments generated using a random number generator; 30 per condition) will be generated by a research coordinator who is not otherwise involved in the project. The slips will be placed into sealed, opaque, and identical envelopes, and these will be allocated to numbered study binders by a study coordinator. Participants will be assigned to a study condition via this simple randomization method initially. Once at least 8 participants have been enrolled in each group (to allow initial population of both groups prior to balancing via minimization), we will activate the minimization procedure. For all subsequent enrollees, allocation of participants to study condition using a dynamic automated minimization algorithm⁵⁵ will occur to ensure balance on dichotomized age, gender, baseline physical activity, and medical comorbidity (Charlson index⁵⁸) variables, using established methods.^{55,57,59} These covariables will also be included in the statistical models used to analyze study outcomes as per published methods using this technique.⁶⁰ No study staff or investigators will be aware of a participant’s condition until consent and all baseline assessments have been completed; participants and study staff will learn of the participant’s study condition contemporaneously (via envelope [initial 16 enrollees] or computer assignment [subsequent enrollees]).

V. Study procedures

A. Study visits/assessments (See Figure, below)

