To measure physical activity, we will use the ActiGraph GT3X+ accelerometer,⁸² a small, silent device without readout that is worn at the hip and stores data for several weeks; it has been validated and used in many populations, including T2D, to measure habitual physical activity.⁸³ The GT3X+ is a half-dollar-sized device that is very lightweight, clips to a belt or

shoe, and has no sharp edges, shock risk, or visible readout (or any identifying data). Participants will wear the devices for 7 days. We will consider 5 valid days of wear (8+ hours per day) to be sufficient; participants will re-wear devices if needed. In a recently completed PP-MI study in ACS patients (n=128; PHS IRB# 2014P001756), we used these devices/methods with good results. Sedentary time will also be measured with Actigraphs, using protocols to differentiate between sedentary time and device non-wear.^{84,85} Data will be downloaded onto our study team's local computers without need to transmit data to external servers.

D. Procedures

A single venous blood sample will be collected at baseline and 8 weeks by study staff trained in phlebotomy, for A1C. No other procedures will be performed.

E. Data collected and when the data is to be collected (see Table 1, below)

Baseline characteristics. To allow us to better understand our study population (and to allow for limited/qualitative accounting for covariates, we will record subjects' baseline characteristics (age, gender, race/ethnicity, duration of diabetes diagnosis, medical and psychiatric comorbidities, medications, and baseline lipids, and hemoglobin A1c). Data will be obtained at the initial interview and supplemented with information from medical records.

Feasibility and acceptability (*Aim 1; # of PP-MI sessions completed, participant ratings of PP-MI ease and utility*). Interventionists will record completion of PP-MI sessions at each session (weeks 1-8). A completed PP-MI session requires both: (i) PP exercise completion and phone discussion, and (ii) the MI portion of the call must end with a specific physical activity-based goal for the next week. In addition, at intervention calls, participants will separately report ease and utility (0-10 scales) of the prior week's PP exercise and MI-based goal-setting, for 4 total ratings per session.

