Physical activity (*Aim 2; moderate to vigorous physical activity (MVPA) and sedentary time, in mean minutes/day*). As noted, we will follow established protocols⁸⁶ for ActiGraphs. Participants will wear the devices for 7 days and we will consider 5 valid days of wear (8+ hours per day) to be sufficient; participants will re-wear devices if needed. We will use standard cutoffs (in counts/minute) for MVPA and non-wear time per the literature^{87,88} and [name]. Sedentary time will also be measured with Actigraphs.^{84,85} This data will be collected at baseline and 8 weeks.

Self-report measures (*Aim 3; psychological, behavioral, and functional measures*). These measures, except for the AUDIT-C and Cigarette Use Questionnaire (baseline only), will be collected by blinded study staff at baseline, 8 weeks, and 16 weeks:

- **Positive affect** (our main psychological outcome given its links to health outcomes and sensitivity to change^{53,65}) will be assessed using the relevant items from the PANAS.⁵⁰
- **Additional psychological measures** will include the well-validated Life Orientation Test-Revised (LOT-R)⁸⁹ for optimism, the Self-Efficacy for Exercise scale⁹⁰⁻⁹² (SEE) for physical activity self-efficacy, and the Hospital Anxiety and Depression Scale (HADS) for depression and anxiety;⁹³ the HADS was designed for medically ill cohorts. We will also include validated measures that may mediate connections between PP-MI and PA; these include the Brief Resilience Scale (BRS), the Self-Efficacy for Exercise (SEE) scale, and the Multidimensional Scale of Perceived Social Support (MSPSS).
- **Overall diabetes self-care** (e.g., diet, medication, foot care), will be measured using we will use the 11-item Summary of Diabetes Self-Care Activities (SDSCA),⁹⁴ a well-

validated self-report measure associated with clinical outcomes.^{95,96}

- For T2D medication adherence, we will use a %-based self-report measure⁹⁷ found to correlate highly with pillcap measurement in T2D patients, allowing us to include patients with varied medications/dosing schedules.
- For dietary adherence, we will analyze the dietary items in the SDSCA as a separate outcome.⁹⁵
- For physical function, the PROMIS 20-item short form (PF-20) will be used. The PF-20 has strong item clarity,⁹⁸ and it has been highly responsive to change in patients with a wide range of physical function.⁹⁸⁻¹⁰⁰
- For pain-related disability, we will use the Pain Disability Index (PDI), validated in medical settings.

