- For self-reported physical activity, we will use the IPAQ, well-validated in diverse settings.
- For self-reported smoking history, we will use the Cigarette Use Questionnaire.
- For self-reported alcohol use, we will use the Alcohol Use Disorder Identification Test – Consumption (AUDIT-C).

Medical outcomes (*Aim #3; exploratory*). At baseline and follow-up, we will also measure weight and A1C.

Table 1. Schedule of study events/assessments.

	Pre-enrollment	Enrollment	Weeks 1-8	Week 8	Week 16
Assessment for inclusion criteria (T2D, IPAQ)	X				
Assessment for exclusion criteria (e.g., cognitive screen, other medical conditions limiting activity)	X				
Interview and chart review for baseline characteristics		X			
Self-report measures		X		X	X
Vital signs (weight) and A1C*		X		X	
Accelerometer (MVPA and sedentary time)		X		X	X
PP-MI exercise sessions			X		
Session ratings by participants (ease/utility)			X		

*Will use values from clinical visit (or within 3 weeks in the case of A1C) if available.

VI. Biostatistical analyses:

A and B. Specific data variables and study endpoints

Specific Aim 1 (*feasibility and acceptability*): To determine whether the PP-MI intervention is feasible (assessed by % of total PP-MI phone sessions completed) and well-accepted (assessed by participant ratings of the ease and utility of each PP-MI session) among T2D patients with low baseline activity.

Measures:

- Rates of completion of exercises (recorded by study trainer)

Specific Aim 2 (physical activity): To assess whether PP-MI is associated with larger increases in MVPA, and less sedentary time, on accelerometer at 8 and 16 weeks, compared to MI.

Measures:

- MVPA in mean minutes per day
- Sedentary time in mean minutes per day

Specific Aim 3 (additional outcomes): To explore whether the PP-MI intervention is associated with greater improvements on other psychological, behavioral, and medical outcomes, compared to MI.

Measures:

- Psychological measures: PANAS, LOT-R, SEE, HADS, BRS, MSPSS
- Behavioral measures: SDSCA, % medication adherence, IPAQ, PF-20, PDI
- Medical outcomes: Weight, BMI, and A1C

C. Statistical methods

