All analyses will be performed under the direction of biostatistician [name]. All analyses will be performed using Stata 14.0. Alpha for between-group comparisons will be set at $p=.05$. We will use descriptive statistics (means, standard deviations, proportions for the Aim 1 feasibility/acceptability outcomes. For Aim 2, we will compare between-group improvement from baseline in mean minutes/day of MVPA (and sedentary time) at 8 weeks using a random effects regression model, with a random intercept for each patient, allowing us to include participants with some missing data.¹⁰¹ For Aim 3, we will likewise compare change from baseline on all measures (e.g., self-care, A1C) at 8 weeks, using random effects models. We will secondarily compare outcomes at 16 weeks, and will complete sensitivity analyses by sex. All variables used in minimization (age, gender, baseline MVPA, Charlson index) will be included as covariates in these models as per protocol using this method.⁶⁰ We will also measure pre-post effect size (Cohen's d , defined as change in the outcome measure divided by the standard deviation of the measure across all time points) of PP-MI for each Aim 2/3 outcome. If there are significant between-group differences in physical activity outcomes, we will use mediation analyses¹⁰² to evaluate a pathway from PP-MI to proximal targets (positive affect/optimism/self-efficacy) to physical activity.

D. Power analysis

For our primary aim (feasibility/acceptability), in our prior work, 75% of subjects completed three-quarters of sessions.^{25,35} Using the same rate, with 30 PP-MI participants we will have 80% power (two-sided $\alpha=0.05$, binomial proportion test) to demonstrate that the proportion who complete ≥ 8 of 11 PP-MI sessions is larger than 50% (i.e., a majority). Likewise, mean PP ease/utility scores were 7.8 \pm 1.8 in prior work;³⁵ with $n=30$ (and 4 weekly ratings per participant), we will have 93% power (using a within-person correlation of 0.5 for ratings across exercises) to detect a true mean score of >7.0 on composite ratings. This initial trial is not powered to definitively test group differences on physical activity and other Aim 2/3 outcomes, but it will allow us to gather data on PP-MI's impact on these outcomes at this key early stage.

VII. Risks and discomforts

A. Complications of surgical/non-surgical procedures

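### The plan does not say how each outcome's own baseline enters the Aim 2/3 models; for sedentary time and the Aim 3 outcomes this could cost precision that the collected data would give

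*Combined protocol and SAP*

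**What the plan says.** Section VI.C sets the Aim 2 comparison as "improvement from baseline in mean minutes/day of MVPA (and sedentary time) at 8 weeks using a random effects regression model"; the random effect is a patient-level intercept. It continues: "For Aim 3, we will likewise compare change from baseline on all measures (e.g., self-care, A1C) at 8 weeks, using random effects models". Week 16 is a secondary comparison. The only covariates named are the minimization variables: "All variables used in minimization (age, gender, baseline MVPA, Charlson index) will be included as covariates in these models". Section IV.C agrees. It describes the algorithm as working "to ensure balance on dichotomized age, gender, baseline physical activity, and medical comorbidity" and carries the same variables into the outcome models.

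The baselines needed for a better adjustment are in hand. The self-report measures, apart from two taken only at baseline, "will be collected by blinded study staff at baseline, 8 weeks, and 16 weeks". For A1C, section V.D says "A single venous blood sample will be collected at baseline and 8 weeks by study staff trained in phlebotomy, for A1C". For the medical outcomes, section V.E says "At baseline and follow-up, we will also measure weight and A1C". Table 1 schedules the accelerometer, which gives sedentary time, at enrollment and at weeks 8 and 16.

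The one other remark on covariates is in section V.E, where baseline characteristics are recorded "and to allow for limited/qualitative accounting for covariates". That is not a model term.

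**The concern.** Baseline MVPA is an outcome's own baseline only for MVPA. For sedentary time and every Aim 3 outcome, the stated model adjusts for four other variables and leaves out what is usually the strongest predictor of the follow-up value. Nor does it say whether baseline is subtracted, is a row of the response, or has a mean common to both arms. These choices give different estimates and standard errors.

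Section VI.D justifies Aims 2 and 3 as gathering data on the intervention's effect, and section II looks ahead to a powered trial. With 30 per arm, intervals wider than the data require, and estimates that carry chance baseline imbalance, are a poorer basis for that step. Minimization does not balance the baselines of sedentary time or the Aim 3 outcomes.

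**Working it through.** **Inputs.** From the documents: N = 60, 30 per arm (sections II and IV.C), and the four covariates above. Assumed, because the documents do not give them: correlation r between baseline and follow-up of 0.3 to 0.9; equal SDs at both times unless stated; own baseline uncorrelated with the listed covariates unless stated; complete data. The plan has no variance or power figure for these outcomes to reproduce. Its 80% power for session completion does reproduce (exact binomial 80.3%, 21 or more of 30) but has no bearing here.

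**Large-sample variances.** With unit SD and 30 per arm, the difference in raw change has variance 4(1−r)/30. After own-baseline adjustment, or with a common baseline mean, it is 2(1−r²)/30. At r = 0.5 these are 0.0667 and 0.0500. The share of raw-change variance removed is 1 − (1+r)/2 = (1−r)/2.

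**Reading A: change score as response, listed covariates included.** Own baseline is one added covariate, going from four to five. With p covariates, estimating the coefficients inflates the variance by 1 + p/(N−p−3). The ratio of the two factors is (1+5/52)/(1+4/53) = 53/52, so the share removed is 1 − [(1+r)/2](53/52).

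**Reading B: baseline as a response row, free arm means, covariates as main effects.** With complete data and a random intercept, covariates that do not vary over time cannot alter the group-by-time estimate. It equals the raw difference in change; simulated fits with and without the covariate agreed to about 1e-15. This holds for MVPA too. Moving from there to ANCOVA with own baseline and all four covariates pays for five coefficients: 1 − [(1+r)/2](1+5/52).

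| r | Large sample | Reading A, N=60 | Reading B to full ANCOVA, N=60 |
|---|---|---|---|
| 0.3 | 35% | 33.8% | 28.7% |
| 0.5 | 25% | 23.6% | 17.8% |
| 0.7 | 15% | 13.4% | 6.8% |
| 0.8 | 10% | 8.3% | 1.3% |
| 0.9 | 5% | 3.2% | −4.1% |

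Simulation agrees with both N=60 columns to within about one point. In reading A the confidence interval narrows by about 19%, 13%, 7%, 4% and 1%.

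**Common baseline mean.** Generalized least squares with this constraint gives 0.65, 0.75, 0.85, 0.90 and 0.95 of the raw-change variance. A plan that meant this model has nothing to recover.

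**Covariate correlated with own baseline (reading A only).** If baseline sedentary time correlates q = −0.5 with baseline MVPA (assumed), the large-sample share is 1 − (1−r²)/[(1−r)²(1−q²) + 1 − r²] = 28.8%, 20.0%, 11.7%, 7.7% and 3.8%. Simulated at N=60 it is about 28%, 19%, 10%, 6% and 2%. In reading B there is no such reduction.

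**Unequal SDs.** With k = baseline SD / follow-up SD, the large-sample share is 1 − (1−r²)/(1+k²−2rk). For k = 0.8 to 1.2 it is 11–40% at r = 0.5 and 0–31% at r = 0.8. At r = k = 0.8 it is 1 − 0.36/0.36 = 0, so at N=60 the extra coefficient costs about 2%.

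**Chance imbalance.** One standard error of the baseline difference is √(2/30) = 0.26 SD. It shifts the raw-change estimate by (1−r) × 0.26 = 0.18, 0.13, 0.08, 0.05 and 0.03 SD, and an own-baseline-adjusted estimate by about 0.

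**Entering a baseline twice.** In one simulated data set at r = 0.5, with own baseline kept as a response row and also entered as a covariate, the estimate did not move but its reported standard error fell from 0.238 to 0.221. That is apparent precision only. The plan's wording allows this for MVPA.

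**The case against.** The strongest reply is that the plan is open, not wrong. The covariate sentence does not exclude other terms, and a random-effects model with a common baseline mean is compatible with section VI.C and loses nothing. This stands: a reader might infer that the plan commits to unadjusted change scores, and the text does not go that far. But neither own-baseline adjustment nor the constraint is stated, and both ordinary readings of the text, A and B, lead to a less efficient estimate at low to moderate r.

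A second reply is that the consequence is small. This also stands. Raw change is unbiased over randomization, and its standard errors are valid. The outcomes are secondary or exploratory, and section VI.D says that the trial is not powered for them. For very stable measures such as weight (if r = 0.95) the large-sample gain is only 2.5%. A reader might infer bias or an inflated error rate from the omission; the documents do not support that.

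A third reply is that adjustment is not always a gain. Correct: when r is high, or baseline SD is well below follow-up SD, it can cost about 2–4% of the variance at N=60.

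Two further inferences should be resisted. One is that MVPA is exempt because its baseline is a listed covariate; that is so only when the response is a change score. The other is that the source of baseline MVPA is unknown, so that the IPAQ outcome might already have its own baseline in the model. Section V.A has the accelerometer worn before visit 2 to measure baseline activity, and randomization falls at visit 2, so the accelerometer is the natural reading.

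**Conclusion.** The point holds as an under-specified model with a readily available improvement, at low severity. The omission is plain in sections IV.C and VI.C. Its size depends on how the model is built. It is about 34% to 3% of the variance at N=60 for r = 0.3 to 0.9 under a change-score response, and (1−r)/2 in large samples (35% to 5%) where baseline is a response row with free arm means. In that second case the realizable gain at N=60 runs from about 29% down to a loss of about 4%. It is zero under a common-baseline model. All of this rests on assumed r, equal SDs and complete data, and on own baseline being uncorrelated with the listed covariates. No percentage can be read as a property of the plan itself. Confidence is high for the omission and only illustrative for the magnitude.

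**What to change.** State in section VI.C, before outcome data are examined, how baseline enters each Aim 2/3 model:

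- For outcomes measured at weeks 8 and 16, model the follow-up values on the outcome's own continuous baseline, the minimization variables and group-by-visit terms, with a patient random intercept.
- For A1C, weight and BMI, which have one follow-up at week 8, use ANCOVA of the week 8 value on own baseline, group and the minimization variables.
- Alternatively, specify a repeated-measures model with a baseline mean common to both arms.
- In either case enter each outcome's baseline only once, including for MVPA.

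The cost is one paragraph and a small change in model code, with no new data. The statistical price is one further coefficient per model (about 2% of the variance at N=60). In the least favorable case tabulated, r = 0.9 compared with raw change, the full set of five covariates costs about 4%.

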I. Background

A. Historical Background

Physical inactivity among patients with type 2 diabetes (T2D) is a major clinical and public health problem. Roughly 18 million Americans with T2D do not follow recommended guidelines for physical activity,¹ and inactivity is independently associated with major diabetes-related complications and mortality.²⁻⁴ Intensive multicomponent programs for physical activity and other health behaviors in T2D have had positive results in research trials but may be less feasible and effective when applied in front-line clinical settings.⁵⁻⁸

Motivational interviewing (MI) is a more widely applied technique that can improve physical activity in T2D. MI is a patient-centered approach used to address ambivalence and promote change,⁹ and it can be effectively delivered in person and by phone.¹⁰⁻¹² MI can be used with patients at any stage of change, from those who currently are not ready to become active, to those who are highly motivated to make change.⁹ MI has been used in many settings for >30 years and has resulted in increased physical activity in patients with T2D.¹³ However, MI alone may not be enough. Though MI is associated with increased physical activity in T2D, the effect size has been relatively small (~0.2 in 3 recent trials),¹⁴ and these somewhat limited effects on physical activity may not translate to fewer adverse clinical events. Also, specific subgroups may be less likely to benefit from MI, such as those who have low expectation of improvement, low overall optimism, or low perceived social support.¹⁵⁻¹⁷ Fortunately, MI has integrated well with other treatments in research and clinical settings.^{18,19}

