Positive psychological states and physical activity. In 164 patients with an acute coronary syndrome (ACS), we found that optimism 2 weeks post-ACS predicted greater 6-month physical activity (measured by accelerometer), controlling for baseline physical activity, medical factors, sociodemographics, depression, and anxiety ($\beta=102.5$; $p=.026$).³² We also completed a mixed methods project with ACS patients (N=32), finding that optimism and positive affect led to initiation of physical activity and predicted overall future health behavior adherence.^{33,34}

PP intervention studies in cardiac patients. We tested PP in two controlled trials in patients with heart disease. In a small pilot (N=28), PP was associated with more improvement in mental health outcomes than either attentional control or mindfulness interventions.²⁵ We then used the above qualitative interviews to refine the PP intervention and studied the revised intervention in 48 post-ACS patients. The intervention was well-accepted and led to improvements in psychological status (positive affect, depression, and anxiety), compared to usual care.³⁵ We are now examining the effects of PP on activity after ACS.

PP-MI intervention studies. In concert with [name], who has much experience testing MI in medical cohorts,¹⁰⁻¹² we have developed a combined PP-MI intervention that is now being studied in a trial (N=128) comparing PP and PP-MI for ACS patients with low physical activity.³⁶ In the first 50 participants, both conditions were associated with increases in physical activity. However, PP-MI participants had even greater physical activity improvement (12.6 metabolic equivalent [MET]-hours; effect size difference: $d=.33$) at 16 weeks, compared to PP. This data further supports the idea that PP, and especially PP-MI, can improve physical activity in medical populations.

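### Mediation is run only after a significant activity difference that the pilot is not powered to detect, so the indirect effect may go unreported

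*Combined protocol and SAP*

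**What the plan says.** Section VI.C makes the mediation analysis conditional: "If there are significant between-group differences in physical activity outcomes, we will use mediation analyses". Its purpose is "to evaluate a pathway from PP-MI to proximal targets (positive affect/optimism/self-efficacy) to physical activity". The condition does not say which activity outcome counts (accelerometer MVPA, sedentary time, or the self-reported IPAQ listed under Aim 3) or at which time point. No mediation analysis is described for a non-significant result, and no time points are given for the mediation model.

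Section VI.D states that "This initial trial is not powered to definitively test group differences on physical activity" or the other Aim 2 and 3 outcomes. The trial is instead meant to gather data on PP-MI's "impact on these outcomes at this key early stage".

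The mediators are analysed by arm in any case: "For Aim 3, we will likewise compare change from baseline on all measures". The main comparison is at 8 weeks, and "We will secondarily compare outcomes at 16 weeks".

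On timing, section V.A (Follow-up assessments) has participants wear the accelerometer for a week and then attend the 8-week visit, where self-report data are taken. The 16-week accelerometer measurement appears in Aim 2 (sections II and VI.A and B), in section V.A (Overview and Follow-up assessments) and in Table 1. The physical activity paragraph of section V.E lists only baseline and 8 weeks.

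**The concern.** A non-significant activity difference in 60 patients says little about whether an indirect path exists. Making the mechanism estimate depend on that test means it may never be produced, although positive affect, optimism, self-efficacy and activity are all measured regardless. Aim 3 supplies the treatment-to-mediator effects but not the mediator-to-activity link, and that link is what the condition withholds. Section II says the expected results would justify a well-powered efficacy trial, and an indirect effect with its interval would help plan one.

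There is a second, smaller cost. When the condition is met, the activity estimate has been selected for being large. Because the condition names no outcome or time point, whether it is met could also turn on a choice made after the data are seen.

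**Working it through.** **1. The plan's own figures.** The plan gives no power for the activity comparison; both stated powers concern Aim 1. The feasibility power reproduces: with n = 30, a null of 50% and a true rate of 75%, rejecting at 21 or more completers has upper-tail probability 0.0214 and power 0.803, against 80% stated.

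**2. Inputs for the gate.**
- 30 per arm (section IV.C) and alpha 0.05 (section VI.C). Two-sided is assumed, as in section VI.D.
- d = 0.2: for MI in type 2 diabetes, section I.A says "the effect size has been relatively small".
- d = 0.33: from PP-MI against PP in acute coronary syndrome, where section I.B reports "PP-MI participants had even greater physical activity improvement".
- d = 0.5: assumed. It is included because section V.A expects the control condition to do little for activity.
- r, the correlation of the outcome with its baseline: assumed 0, 0.5 or 0.7.

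**3. One test.** The noncentrality is d/√(1−r²) × √(30/2), with 58 degrees of freedom at r = 0 and 54 with the four planned covariates. For d = 0.33 it is 0.33 × 3.873 = 1.278 at r = 0, 1.476 at r = 0.5 and 1.790 at r = 0.7.

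| True d | Gate opens, r = 0 / 0.5 / 0.7 | Mean significant positive d | Ratio to truth |
|---|---|---|---|
| 0.2 | 0.119 / 0.142 / 0.187 | 0.63 / 0.55 / 0.46 | 3.1 to 2.3 |
| 0.33 | 0.242 / 0.305 / 0.420 | 0.66 / 0.58 / 0.50 | 2.0 to 1.5 |
| 0.5 | 0.478 / 0.593 / 0.759 | 0.71 / 0.64 / 0.57 | 1.4 to 1.1 |

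The last two columns concern the total activity effect, not the indirect effect.

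**4. Several tests.** Suppose MVPA or sedentary time at 8 or 16 weeks can each open the gate (four tests, equal d, assumed correlation between tests 0.3-0.7, r 0-0.7). Simulation then gives 26-48%, 45-80% and 72-98% at d = 0.2, 0.33 and 0.5. With two tests it gives 18-31%, 34-62% and 61-91%.

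**5. The indirect effect at 8 weeks.** Assumed paths: treatment to mediator 0.5, mediator to 8-week MVPA 0.3, direct effect 0.18. The indirect effect is 0.5 × 0.3 = 0.15 and the total is 0.15 + 0.18 = 0.33. The model adjusts for baseline mediator and baseline MVPA. The scale is that of the simulation, where the within-arm SD of 8-week MVPA is √1.09 ≈ 1.04.

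Over r = 0 to 0.7 the estimate averages 0.15 with a standard error of 0.09-0.11. A hand check at r = 0 uses SE(a) = √(2/30) = 0.258 and SE(b) ≈ 1/√55 = 0.135:

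√(0.3²×0.258² + 0.5²×0.135² + 0.258²×0.135²) ≈ 0.108.

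When 8-week MVPA is significant the estimate averages about 0.16-0.18, which is 1.1-1.2 times the truth. When it is not, the average is about 0.14. A rough normal interval is 0.15 ± 1.96 × 0.11, or −0.07 to 0.37. With a standard error of 0.09 it is −0.03 to 0.33.

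**6. A lagged alternative.** This model takes 8-week mediators to 16-week MVPA, adjusted for 8-week MVPA. If a further mediator-to-16-week path of 0.3 is assumed, it also averages 0.15, with a standard error of about 0.11. If that path is set to zero and the 0.15 at week 8 is kept, the lagged estimate averages 0.00 at every r, while the 8-week model still recovers 0.15.

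**The case against.** The plan discloses its limited power, and saying that a trial cannot test a difference definitively does not forbid testing it at 0.05. A reader might infer that the plan contradicts itself; it does not. Requiring a group difference before modelling its mechanism is a recognised choice. With three mediators, two accelerometer outcomes and two time points in 60 patients, it limits fishing. That argument has some force, and it is why ungated estimates should be few, pre-named and labelled exploratory.

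A reader might also infer from the 2.3-3.1 ratio that mediation estimates would be grossly overstated. That ratio belongs to the total activity effect at d = 0.2; the indirect effect moves far less (step 5). Nor do the documents show that the gate will nearly always stay shut. The condition refers to outcomes in the plural and fixes no time point, so under the widest reading in step 4 it opens in 26-98% of trials.

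Finally, the lagged model is tempting as the main analysis because, in the 8-week wave, activity is recorded before the mediators are reported. But section VI.C asks about the pathway to activity, and its main comparison is at 8 weeks. The lagged model blocks whatever mediation has already appeared in 8-week activity, so it can return a null when the hypothesis is true. It is suitable only as a sensitivity analysis.

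What survives is that a mechanism estimate from data already in hand should not depend on an underpowered and loosely defined test.

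**Conclusion.** The point holds as a minor design weakness. On a single test the gate opens in 12-19%, 24-42% and 48-76% of trials at d = 0.2, 0.33 and 0.5, and more often if several tests count. The actual rate cannot be fixed, because the plan does not define the gate and no cited effect size compares PP-MI with MI in type 2 diabetes. The main consequence is possible non-reporting of the indirect effect; inflation of about 1.1-1.2 times is secondary. All baseline correlations, path values and between-test correlations are assumptions. Treatment effects on the mediators are reported under Aim 3 regardless, mediation is in none of the three aims, and Aim 1 is unaffected. Priority is low; the reason to act is that the change costs almost nothing.

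**What to change.** In section VI.C:
- Delete the significance condition. Report the indirect effects through positive affect, optimism and self-efficacy with confidence intervals, labelled exploratory, whatever the group difference.
- Use 8-week mediators and 8-week accelerometer MVPA, adjusted for baseline mediator and baseline MVPA. State that this same-wave model cannot establish direction.
- Optionally add 8-week mediators on 16-week MVPA, adjusted for 8-week MVPA, as a sensitivity analysis only. State that it captures only effects arising after week 8 and would be expected to be null if mediation is complete by then.

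Separately, reconcile the physical activity paragraph of section V.E (baseline and 8 weeks) with Aim 2, section V.A and Table 1, which include week 16. The planned 16-week activity comparison depends on this whether or not mediation is run.

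The cost is a few sentences of wording, with no new data, visits or participants. The downsides are wide intervals (standard error about 0.09-0.11 for an indirect effect of 0.15 under the assumed paths) and several mediator estimates that must be read with caution, as estimates and not as tests.
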